	Policy-maker/Admin Interview Guide – Informational
Aim 3	
Disclosure outcome	Disclosure Checklist
	Disclosure Readiness assessment
Transition outcome	Transition Tracking Log
	Transition booklet tracking
	Transition readiness assessment (HCW)
	Transition readiness survey (adolescents)
Pre-trial surveys	Pre-trial Adolescent Survey
	Pre-trial HCW Survey
Implementation period	HCW FGD Guide
	HCW implementation survey
	HCW PDSA Worksheet
	HCW FGD Demographic Form
Post-trial IDIs	General - Adolescent Demographic Form
	Post-Trial Adolescent Interview Guide – Disclosure Focus
	Post-Trial Adolescent Interview Guide – Transition Focus
	General - HCW Demographic Form

	Post-Trial HCW Interview Guide
	Post-Trial ATTACH Staff Interview Guide
Post-trial surveys	Adolescent Survey
	HCW Survey
COVID-19 Adapted Forms	CQI Phone Delivery Script
	Transition Readiness Assessment Delivery Script
	Transition Intervention Delivery Script

Consent Forms:

Study Activity	Consent document
Aim 1	
Facility Survey	Consent for facility survey
Aim 2	
Adolescents in HIV care (48 not completed transition, 48 effectively transitioned)	Adolescent Assent (Age 14-17) for Focus Group Discussion
	Parental consent for Adolescent Informational Focus Group Discussion (Age 14-17)
	Consent for Adolescent Informational Focus Group Discussion (Age 18-24)
Caregivers	Consent for Caregiver Informational Focus Group Discussion
Policy makers	Consent for Policy maker Informational Interview
HCW/Administrator	Consent for HCW/Administrator Informational Interview
Working group	Consent for HCW Working group
Aim 3	
Pre-Trial Surveys	Oral consent for anonymous Adolescent Pre-Trial Survey (age ≥18)
	Oral assent for anonymous Adolescent Pre-Trial Survey (ages 12-17)
Implementation Activities	HCW IS Activities Consent Form
Post-trial IDI	Adolescent Assent (ages 14-17)*
	Consent for Adolescent Post-Intervention IDI (Age 18-24)
	Parental Consent for Adolescent Post-Trial IDI (Age 14-17)
	Consent for HCW Post-Trial IDI
Implementation FGDs	HCW Implementation FGD Consent Form
Transition readiness surveys	Assent and Consent Form for Adolescent Transition Readiness Assessment Survey (10-24 years old)
Disclosure readiness surveys	Caregiver consent for disclosure readiness survey
Post-trial surveys	Oral consent for anonymous Adolescent Post-Trial Survey (age ≥18)
	Oral assent for anonymous Adolescent Post-Trial Survey (ages 12-17)
	Oral consent for anonymous HCW Post-Trial Survey

*Same as aim 2 document

Recruitment Scripts:

Study Activity	Recruitment Script
Aim 1`	
Facility Survey	Facility Survey Recruitment Script
Aim 2	
Adolescents in HIV care (48 not completed transition, 48 transitioned)	NA
	Caregiver recruitment script for adolescent IDI and FGD
	Adolescent recruitment script
Caregivers	Caregiver recruitment script
Policy makers	Policy maker/Admin/HCW recruitment script
HCW/Administrator	Policy maker/Admin/HCW recruitment script
Working group	HCW recruitment script for Workshop
Aim 3	
Pre-Trial surveys	Adolescent Recruitment Script*
Implementation Activities	HCW IS Activities Recruitment Script
Post-trial IDI	NA
	Adolescent recruitment script*
	Caregiver recruitment script*
	HCW recruitment script*
Implementation FGDs	HCW FGD Recruitment Script
Transition readiness	Adolescent recruitment script*
Disclosure readiness	Caregiver recruitment script
Post-trial surveys	Adolescent recruitment script*
	HCW recruitment script*

*Same as aim 2 document

ATTACH STUDY ANALYSIS PLAN (Finalized 2.13.2020)

SUMMARY

Study Purpose: To determine whether an adolescent transition package (with transition and disclosure tools) improves **mean transition readiness** among HIV positive adolescents in care in Kenya.

Study Design: Cluster randomized trial

Study Population and Sites:

Population:

- HIV-positive adolescents and youth between the ages of 10 and 24

Sites:

- 20 HIV clinics in Nairobi, Nakuru, Homabay and Kajiado, Kenya

Study Duration: Estimated 18 months total (enrollment and 1-year follow-up)

Randomization: 10 clinics randomized to intervention sites and 10 to control.

Intervention:

Adolescent Transition Package (ATP): The ATP will consist of a validated disclosure booklet and disclosure tracking tool, and a HCW administered transition booklet and transition tracking logs, implemented in intervention sites. HCW in intervention sites will be trained on implementation of the ATP with continued support for the clinic in the first 3 months of the intervention. In control sites, parallel data collection for primary outcomes will be conducted.

Primary endpoints: Transition readiness

Secondary endpoints: Overall clinic retention and overall viral suppression

Exploratory outcome: % with full disclosure, Time to full disclosure, Post transition retention

DATA ANALYSIS

Primary outcome: transition readiness among HIV positive adolescents age 15-24

- a. Transition readiness score overall (all domains)
- b. Treatment literacy readiness score
- c. Self-management readiness score
- d. Communication readiness score
- e. Support readiness score

Analysis

Primary analysis ITT: Mixed effects linear regression to compare transition readiness scores (overall and by domain) over time in control and intervention sites with adjustment for multiple testing (Benjamin-Hochberg method).

Time points: Enrollment, month 6, month 12

Sample size and power table

Assumptions: 80% power, alpha 0.05, ICC 0.2, average cluster size of 50

Mean difference	SD	Number of Clusters per Arm
0.5	1	4
0.5	2	15
1.0	2	4
1.0	3	9
1.5	3	4
1.5	4	7
2.0	5	6
2.0	6	9

Secondary outcomes

- a. Overall retention in 10-24 year olds: defined as proportion of 10-24 year olds completing visits within 6 months of last visit
- b. Overall viral suppression: defined as proportion of 10-24 year olds with viral load of less than 1000 copies per ml after at least 6 months of ART

Analysis

Overall retention/suppression: Generalized estimating equations (GEE) to compare retention and viral suppression in intervention and control sites

Time-points: Baseline, month 6, month 12

Minimum detectable differences in proportions with outcomes

Assumption: 80% power, alpha 0.05, ICC 0.2, 10 clusters per arm, average cluster size of 50

Proportion with outcome in arm 1	Proportion with outcome in arm 2
0.2	0.31
0.3	0.44
0.4	0.56

0.5	0.69
0.6	0.81
0.7	0.93

Exploratory analyses

1. Post-transition retention defined as completing and adult clinic visit day after transfer to adult services and at least 1 other visit within 6 months of the adult visit (total of 2 visits):
Analysis: GEE to compare post-transition retention in intervention and control sites
2. Principal components analysis to identify the most representative components of data in the 4 domains of the readiness assessment checklist (HIV treatment literacy (Q 1-5), self-management (Q6, 7, 9-14, communication Q16-19, support 20-22) and then factor analysis to determine the most important components.
3. Proportion of children with full disclosure and time to full disclosure. Children who do not know their HIV status from HCW assessment. Child will be asked why they are taking medicine; if they report they have HIV they have reached full disclosure. If they mention any other illness or other responses they will not have reached full disclosure.
End point: Child says they have HIV in response to the question “why are you taking your medicine”
Analysis: Descriptive %, time to full disclosure

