The disclosure tool includes a cartoon book, readiness and tracking tools used in clinic and a HCW training. The intervention progresses from incomplete to complete disclosure using a narrative about soldiers fighting the battle of infection as the rationale for taking medicine. This tool has been validated for use in Namibia.

The Got Transition model is based on health care perspectives of adolescents, caregivers, and providers and program evaluations in the US. It has 6 core elements that were iteratively developed and offer a standardized approach that can be used in varied settings (Table 5). The Core Elements address inter-related health systems components relevant to diverse HIV programs in Kenya. The Transition tools for the ATP include a transition flipchart, readiness assessment, and transition progress tracking tool. In addition, the study team will develop training materials to support the implementation of the transition tools.

Table 5: Core elements of the Got Transition Program

6 Core Elements of Got Transition Program	
	Selected key concepts
Transition policy	Develop clinic policy on transition Educate and post policy
Transition tracking and monitoring	Criteria for identifying eligible adolescents Tracking registry/tool development
Transition readiness	Regular transition discussions starting age 14 Develop prioritized actions (joint adolescent/caregiver)
Transition planning	Regular planning, goals re: timing of transition
Transfer of care	Confirm date, assess self-care readiness
Transfer completion	Elicit feedback regarding transfer, follow-up retention

The validated Namibia booklet and the Got Transition tool can be found in the appendices.

Each clinic team in the intervention sites will implement the tools guided by the study team with twice-monthly check-ins and evaluation. The twice-monthly check-ins will use modified PDSA cycle materials to facilitate feedback and adaptations to optimize ATP implementation.

The study will aim to optimize implementation of ATP over a 6-month period at each intervention site with continued clinic support throughout the course of implementation and measure the effect of the well-implemented ATP on transition outcomes over a 2-year period.

SECTION 7: STUDY PROCEDURES

COVID-19 ADAPTED STUDY PROCEDURES

As a result of the COVID-19 pandemic and resultant changes to visit schedules and client contact time, we propose the following changes to study procedures during the pandemic period:

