All caregivers of children and adolescents ages 6-19 years who have not yet attained full disclosure and are attending clinic visits at intervention sites will be eligible to participate in the surveys. Caregivers will be recruited during clinic visits by a member of the study team or by phone prior to returning to clinic for their child's study visit. A recruitment script with guiding information is provided in the appendices. If a caregiver is interested in participating, eligibility will be assessed by clinic or study staff by asking a series of questions. These questions will confirm that the caregiver is someone responsible for caring for the child and that the child or adolescent does not know their HIV status. Example questions that study staff might ask include: "how old is the child you bring to this clinic," "does the child know that they have HIV" and "are you this child's primary guardian."

Caregivers who meet eligibility criteria and are interested in participating will give written consent to participate in the surveys. Caregivers will be informed that their data will be linked to their child's medical record data, but this survey will not contain their name, only their ID. All caregivers who provide consent will be enrolled and participate in this survey. Caregivers who provide consent will take the disclosure readiness surveys every 6 months and will receive 600 KES for completing the survey each time.

Data collection procedures:

The study is not blinded and clinic leadership will be informed of the allocation, either to intervention or no intervention. For both groups, the study team will conduct study specific training. For intervention sites, training will include the use of the disclosure tools, transition tools and other study data collection material. Control sites will undergo training on collection of study related data.

Intervention clinics: The study will aim to optimize implementation of the ATP over the 6-month period at each intervention site and will measure the effect of the well-implemented ATP on transition over a 2-year period.

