- a. Recruitment to participate in anonymous survey
- b. Oral consent or assent
- c. Complete survey

Post-Trial procedures- Control sites:

At the end of the trial control sites will be offered study tools used in the intervention sites and will be offered training on how to use them. Any material developed including tracking tools will be shared with the control sites to allow them to use tools they find useful. Results of the trial will be presented to all sites in site close-up meetings.

7e. Assessment of participant compliance with study intervention

We will regularly monitor turn-over of trained HCWs, changes in clinic policies and procedures, and other facility-level factors that could affect intervention fidelity.

SECTION 8: STUDY SCHEDULE

An overview of the anticipated overall study schedule for is shown in Table 6a and 6b (by aim). The study will be conducted over five years. AIM 1 will be implemented in year 1. In year 2 we will complete and disseminate results of AIM 1 and complete AIM 2 and select sites for cRCT in AIM 3 as well as finalize adapted transition tool. In Y3 we will initiate the RCT with 2-year follow-up to be completed by mid-Y5. The final 6 months of the study will be used for manuscript preparation and dissemination of results of AIM 3 to community and global stakeholders.

Table 6a: Overall study schedule: 2016-2021

	Y1				Y2				Y3				Y4				Y5			
	Q1	Q2	Q3	Q4	Q1	Q2	Q3	Q4	Q1	Q2	Q3	Q4	Q1	Q2	Q3	Q4	Q1	Q2	Q3	Q4
Study Planning																				
Protocol development	■	■																		
IRB Submissions		■	■																	
Implementation																				
Site selection		■	■																	
EMR data extraction for AIM 1				■																
Facility surveys				■																
IDIs for adapt				■	■															
HCW workshop						■														
HCW FGD to adapt								■												
Site randomization								■												
Pre-trial surveys								■												
Study training								■	■											
RCT										■	■	■	■	■	■	■	■	■	■	■
Data pull									■								■	■		
Post-trial surveys																	■	■		
Evaluation IDIs																	■	■		
Analysis																				
Data Analysis			■							■									■	■
Dissemination																				
Reports to stakeholders				■															■	■
Manuscript development				■															■	■

Figure 6b: Study timeline by aims

	Year 1		Year 2		Year 3		Year 4		Year 5	
	P1	P2	P1	P2	P1	P2	P1	P2	P1	P2
Develop study material and ethical approval	x	X								

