- We assume that 100 of these eligible clients will be aged 6-15 and that the rate of complete disclosure will be 15% in the control clinics based on our prior studies and the literature with increased prevalence per year of age in this age-window.
- We assume that 100 of these eligible clients will be aged 15-24 years and that 20% (n=20) will be receiving care in a pediatric program and could be eligible to transition (200 per RCT arm). During 2-year follow-up, we anticipate that in the control arm 20% will transition and 10% will transition effectively.

With 10 intervention and 10 control sites, we will have sufficient power to detect an increase in proportion of adolescents with disclosure from 30% to 50%, an increase in proportion who initiate transition from 50% to >80%, and an increase in proportion with effective transition from 10% to 20%. This assumes alpha of 0.05, 80% power, and a conservative estimate of the coefficient of variation of 0.3 (Table 6). Heterogeneity between clusters is expected to decrease with control for baseline testing rates, leading to increased power beyond that which is noted above.

Table 8: Power and sample size ranges

	Outcome Control	Outcome Intervention	Number of clinics per RCT arm to detect difference
Age 10-15	N=1000 (100/clinic)	N=1000 (100/clinic)	
Disclosure process started (proportion)	50% 50% 50%	>80% >90% 100%	9 6 5
Disclosure complete (proportion)	30% 30% 30%	50% 70%	8 4 3
Disclosure age median	14 years old	12 years old	NA
24-month LTFU	20%	10%	7
Age 16-24	N=1000 (100/clinic)	N=1000 (100/clinic)	
Transition discussed (proportion)	20% 20% 50%	40% 60% 100%	6 3 5
Transition complete (proportion)	10%	20%	7
Transition satisfaction	50%	70%	NA
24-month LTFU	25%	15%	10

For the provider and adolescent IDIs, we will select healthcare providers and adolescents from ATP-implementing clinics for individual interviews. Clinics will be purposively selected from among all ATP-implementing clinics. We will purposively select clinics for interviews based on performance, including high and low performing sites as appropriate based on the outcome of the intervention. If the majority of clinics do well, we will purposively select a higher proportion of low performing clinics to understand why they had challenges. If the majority of the clinics do poorly, we will purposively select a higher proportion of high performing clinics to understand how they succeeded.

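### Aim 3 follow-up is two years in the protocol and one year in the SAP, so Table 8's 24-month and 2-year rates cannot be observed on the SAP's schedule

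*Combined protocol and SAP*

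**What the plan says.** **Protocol, two years.** Section 6 says the study will "measure the effect of the well-implemented ATP on transition outcomes over a 2-year period". Section 7c, on intervention clinics, says it "will measure the effect of the well-implemented ATP on transition over a 2-year period". Section 8 says: "In Y3 we will initiate the RCT with 2-year follow-up to be completed by mid-Y5". Section 11a ties the control rates to the same period: "During 2-year follow-up, we anticipate that in the control arm 20% will transition and 10% will transition effectively".

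Table 8 has two rows labelled as 24-month LTFU: 20% v 10% at ages 10-15 (7 clinics per arm) and 25% v 15% at ages 16-24 (10 clinics per arm). Its transition-complete row is 10% v 20% (7 clinics). Section 11a concludes "With 10 intervention and 10 control sites, we will have sufficient power" and adds "This assumes alpha of 0.05, 80% power, and a conservative estimate of the coefficient of variation of 0.3".

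**SAP, one year.** The Summary gives "Estimated 18 months total (enrollment and 1-year follow-up". The primary and secondary analyses use enrollment (baseline), month 6 and month 12 only. Appendix 1 has no column after month 12.

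**Definitions also differ.** Protocol Section 3 counts a transition as effective if visits continue for at least 6 months afterwards. The SAP's exploratory post-transition retention needs an adult visit plus one further visit within 6 months of it.

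**The concern.** An outcome defined at 24 months cannot be read from data that stop at month 12. Even the SAP's 18-month total, which includes enrollment, is shorter than two years. The event rates in Section 11a therefore belong to a longer trial than the one the SAP describes. Events are fewer at an earlier stop, and a row with little slack at 24 months may lose its 80% power.

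The protocol still names disclosure, effective transition and transition readiness together as its primary outcome and claims 80% power for disclosure and transition. A reader of both documents cannot tell at which time point the record-based outcomes will be judged. If this is left open until the data are available, the time point could be chosen after results are known.

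**Working it through.** **Inputs.** From protocol Section 11a and Table 8: alpha 0.05 (taken as two-sided, since sidedness is not stated), power 80%, coefficient of variation k = 0.3, m = 100 per clinic in each age band, 10 clinics per arm.

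**Formula** (Hayes-Bennett, unmatched clusters):

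c = 1 + 7.849 × V / (p0 − p1)², where V = p0(1−p0)/m + p1(1−p1)/m + k²(p0² + p1²) and 7.849 = (1.960 + 0.842)².

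Power with 10 clinics per arm = Φ( √[9 (p0−p1)²/V] − 1.960 ).

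**Step 1: reproduce the plan at 24 months.**
- 25% v 15%: V = 0.001875 + 0.001275 + 0.09 × 0.085 = 0.0108. c = 1 + 7.849 × 0.0108/0.01 = 9.48, so 10 clinics (stated 10). Power with 10: 82%.
- 20% v 10%, and 10% v 20%: V = 0.0016 + 0.0009 + 0.09 × 0.05 = 0.0070. c = 6.49, so 7 clinics (stated 7). Power with 10: 95%.

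All 11 legible proportion rows of Table 8 reproduce exactly. The third disclosure-complete row has no legible intervention value and was not tested.

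**Step 2: convert to 12 months.** The documents give no 12-month rates, so each conversion below is an assumption. Constant hazard means 1 − √(1 − p).

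| Outcome | Conversion | Rates at 12 months | c | Clinics per arm | Power with 10 |
|---|---|---|---|---|---|
| LTFU 16-24 | halved | 12.5% v 7.5% | 12.62 | 13 | 69% |
| LTFU 16-24 | constant hazard | 13.4% v 7.8% | 11.15 | 12 | 75% |
| LTFU 16-24 | 70% of 24-month risk | 17.5% v 10.5% | 10.82 | 11 | 76% |
| LTFU 16-24 | 80% of 24-month risk | 20% v 12% | 10.26 | 11 | 79% |
| LTFU 10-15 | halved | 10% v 5% | 8.85 | 9 | 85% |
| LTFU 10-15 | constant hazard | 10.6% v 5.1% | 8.12 | 9 | 88% |
| Effective transition | halved | 5% v 10% | 8.85 | 9 | 85% |
| Effective transition | constant hazard | 5.1% v 10.6% | 8.12 | 9 | 88% |

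**Step 3: effective transition under protocol Section 3.** If visits must continue for 6 months, a 24-month trial can score transitions in months 0-18 and a 12-month trial only those in months 0-6.
- Evenly spread transitions (6/18 of each rate): 3.3% v 6.7%, c = 11.20, 12 clinics, power 75%.
- Constant hazard over the same window, 1 − (1 − p)^(1/3): 3.5% v 7.2%, c = 9.91, 10 clinics, power 80%.

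Under the SAP's two-visit rule this window does not apply. A transition at month 8 with a second visit at month 10 already counts by month 12.

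**Step 4: cluster size for effective transition.** Section 11a expects only 20 clients per clinic who could be eligible to transition, against the 100 used in Table 8. With m = 20 and the 24-month rates, V = 0.0045 + 0.008 + 0.0045 = 0.0170 and c = 14.34, so 15 clinics. Power with 10 is 63%, before follow-up is shortened at all.

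**The case against.** The strongest reply is that the SAP does not rely on Table 8. It makes the readiness score primary, has its own power tables (ICC 0.2, 50 per cluster), and its Summary lists disclosure and post-transition retention as exploratory. It has no LTFU endpoint and no split at ages 10-15 and 16-24; it analyses retention in all 10-24 year olds. On this view Table 8 is detached mainly because the endpoints changed. That stands, and it limits the consequence. It does not remove the contradiction, because the protocol still carries the two-year follow-up, its primary outcomes and its power claim. Nor can the protocol be dismissed as an old text: it is signed April 2018 but contains COVID-19 procedures, so it has been revised since, and it still says two years. Neither document says which governs.

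A second reply is that the LTFU loss is modest and could be recovered. Section 11a expects baseline adjustment to reduce heterogeneity. At k = 0.25 the constant-hazard LTFU rates at ages 16-24 give c = 9.49 and 82% power. That is fair, but the protocol states no reduced k, so this too is an assumption.

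A reader might infer that effective transition also becomes underpowered at 12 months, at about 75%. The documents do not support that as a finding. The figure needs the Section 3 definition together with evenly spread transitions; the other conversions give 80-88%, and the SAP uses a different rule.

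**Conclusion.** The inconsistency is explicit and unreconciled, and should be corrected. The 24-month LTFU rows and two-year transition rates cannot be observed on a schedule ending at month 12, whatever conversion is assumed.

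The size of the power loss does depend on assumption. Only LTFU at ages 16-24 falls below 80% under every conversion tried at k = 0.3 and m = 100: from 82% to about 69-79%. For effective transition no shortfall from follow-up length is established. Disclosure rates have no stated time horizon, so nothing follows for them.

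Two stronger readings should be resisted. Table 8 is not miscalculated: it reproduces at 24 months. Nor does this point show that the trial loses power for the SAP's primary endpoint, whose power table takes no follow-up length as an input.

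**What to change.** Adopt one follow-up length for Aim 3 across protocol Sections 6, 7c, 8 and 11a and the SAP Summary, analysis time points and Appendix 1. Two routes are open.

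1. **Twelve months throughout.** Replace or retire Table 8's 24-month and two-year rows, relabel LTFU as 12-month, and give power as a range with its assumptions. Do not enter 75% for effective transition: Section 11a's own 20 eligible clients per clinic give about 63% even at 24 months, so that row needs its cluster size settled first.
2. **Month 12 for readiness, 24 months for records.** State in the SAP that retention, disclosure and transition outcomes from clinic records and logs are extracted to 24 months, in line with the protocol's two-year follow-up and its plan to abstract records throughout the RCT.

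In either case, choose one definition of effective transition or post-transition retention, and score it only for transitions with enough remaining follow-up to meet it. Record the choice before outcome data are compared by arm.

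The cost is wording in both documents and a recalculated table. Route 2 adds a later record extraction; the protocol already requests a waiver of individual consent for abstracting clinic records. Under route 1 the stated power for LTFU at ages 16-24 becomes less favourable.
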